Treatment Navigation for Opioid Use Disorders

Study Protocol

A113229 [name] (FA130694) (WA State Innovation Initiative- Medication Assisted Treatment upon Release from Prison)

[name], MSW, MPH	Principal Investigator	Alcohol and Drug Abuse Institute	[contact]
[name]	Co-Investigator	General Internal Medicine	
[name]	Co-Investigator	Psychiatry and Behavioral Sciences	[contact]
[name], RN	Co-Investigator	Health Services	[contact]
[name]	Project Director	Alcohol and Drug Abuse Institute	[contact]

Abstract

We will conduct a pilot randomized controlled trial (RCT) study. One hundred inmates with OUD releasing from WA State prisons to community corrections supervision in King County, WA will be enrolled (the county has a population of 2 million residents out of a state population of 7 million). Half of the subjects will receive treatment as usual, for instance outpatient drug counseling, and half will receive 6 months of intervention. The aims of this study are to determine: 1) whether study procedures can be implemented with fidelity, 2) whether offenders can be enrolled and maintained in the study, 3) which medications/treatment options subjects select and their experiences and satisfaction with the interventions, and 4) preliminary intervention effect size on outcomes of interest including recidivism, drug use, hospitalization, and treatment enrollment and retention.

Introduction

One-third of heroin users are incarcerated each year primarily due to criminal activity related to their drug use and *“policy changes and interventions are urgently needed to reduce the negative consequences of opioid relapse following re-entry”* (Fox et al., 2015). The number of heroin users and the number dying from opioid overdoses have increased significantly in recent years across the U.S. while pharmaceutical opioids remain a common pathway into heroin and a persistent overdose risk (Jones et al., 2015; Peavy et al., 2012).

The time shortly after release from prison is a period of greatly increased risk for fatal opioid overdose (Binswanger et al., 2013; Merrall et al., 2010). Opioid use disorder can be readily treated with medication assisted treatment (MAT) reducing criminal activity, recidivism, improving

functioning, decreasing mortality and transmission of infectious diseases like HIV and HCV, and substantially reducing costs (Clark et al., 2011; MacArthur et al., 2012; Nolan et al., 2014; Nordlund et al., 2004; Tkacz et al., 2014; Tsui et al., 2014; White et al., 2014). A major challenge in breaking the cycle of addiction and criminality and related morbidity and mortality is seamlessly getting people onto MAT as they leave incarceration. This is a matter of simultaneously building interest in treatment among newly released inmates and increasing and facilitating access to ongoing services.

Great interest in this topic has been expressed locally as indicated by the January 2016 release of Washington State's Interagency Opioid Workplan, co-authored by Drs. [name] and [name], collaborators on this project. A main strategy in the Workplan is to *"Optimize access to chemical dependency treatment services for offenders who have been released from prison into the community..."*ⁱ. Numerous challenges exist to providing effective services to releasing prison inmates with OUD, including: 1) identification of the population at risk, 2) inmates' often modest knowledge and misperceptions of MAT as well as limited motivation and self-efficacy for accessing treatment, 3) lack of continuity of care between the relatively protected prison environment and effective services in the community and 4) maintaining ongoing utilization of MAT to support recovery and reduced consequences related to opioid use.

[figure not shown]
This innovation initiative, based on evidence-based practices, will develop, implement, and assess the feasibility of procedures to provide effective services for offenders with OUD releasing from WA DOC prisons. We will aim to facilitate linkage to ongoing MAT in the community following release from custody beginning with an initial intervention aimed to educate inmates so they can make informed decisions regarding medication options.

The Affordable Care Act (ACA) has markedly increased eligibility for health insurance coverage for releasing offenders, such that a very high proportion of offenders releasing from WA DOC prisons qualify for Medicaid coverage. Since 2014, WA DOC has launched an effort to enroll as many releasing offenders as possible into Medicaid coverage effective at the time of release resulting in a substantial majority of inmates obtaining Medicaid coverage. We are fortunate that WA HCA (Medicaid) has undertaken several initiatives to promote better integration of healthcare services including integrating medical, mental health, and substance use disorder treatment that should facilitate this study and support sustainability long term (see letter of support).

The crux of this innovation initiative is building motivation and self-efficacy for and ready access to adequate coordinated care for releasing offenders with OUD to initiate and maintain MAT. Given that MAT has the best evidence base for effective treatment of OUD, facilitating access to MAT (accompanied by psychosocial treatment as appropriate) will be the major thrust of the initiative. Our intention is to make appropriate treatment (buprenorphine, methadone, and long-acting-naltrexone) available, with the particular treatment approach selected on a case-by-case basis by the patient and medical provider. We will be working with community based partners who will be providing MAT including, but not limited to [name], co-investigator and Evergreen Treatment Services (see letter of support). These partners will be responsible for all medical and related care

including counseling as indicated, we will be coordinating with them and the study participants to facilitate care.

Study Design

Eligibility Criteria

Inclusion criteria

- 1) Meets DSM-5 criteria for opioid use disorder (at least 2 criteria) or were receiving treatment for opioid use disorder in the 12 months prior to incarceration.
- 2) Released to community corrections, not currently incarcerated.
- 3) Able to understand and provide informed consent.
- 4) Has access to phone (voice or text) or email to communicate with research staff.

Exclusion criteria

- 1) Under age 18 or over age 70 at time of recruitment.
- 2) Currently enrolled in an opioid treatment program using medications.
- 3) Has not used opioids (prescription type or heroin) in the past 6 months prior to incarceration.
- 4) Unwilling to allow access to medical or drug treatment records, criminal history or criminal activity records.
- 5) Inability to communicate in English verbally.
- 6) Inability to provide adequate contact information to assist with follow-up.
- 7) Not planning on being in King County or reporting to community corrections in King County for 6 months.
- 8) Violent or overtly hostile/threatening towards research staff.
- 9) Entering 31 days or more controlled environment in the next 6 months.

Potential Subjects Identified

Recruitment, baseline interviews, and some follow-up interviews (if convenient for the subject) will take place in community corrections offices (CCOs) throughout King County. We will concentrate initially on offices in Seattle and South King County. Department of Corrections (DOC) will run weekly reports on inmates for upcoming releases to King County CCO facilities. DOC will notify CCO staff that a potential subject will be released to that facility. Once released, we will approach, recruit and enroll them during their first visit at the community corrections office and randomize to treatment as usual or intervention.

Obtain Informed Consent

Written informed consent will be obtained from all subjects who wish to participate in the study. Subjects will also be asked to complete HIPAA authorization agreements for treatment and medical records information and other secondary data sources.

Eligibility Screening

Subjects will be men or women aged 18-70 released from Washington State prisons to community corrections supervision in King county, meeting at least mild severity for Diagnostic and Statistical Manual of Mental Disorders Fifth Edition (DSM-5) criteria for diagnosis for opioid use disorder (e.g.

opiate dependence). Subjects will be asked to complete an eligibility screening questionnaire. The items covered are general demographics, proximity to the research settings, drug use questions, and DSM 5 checklist.

Baseline Assessments

Eligible subjects will undergo baseline assessments and provide information on personal information and health:

- 1) Opioid Use and Treatment Experiences: This assessment captures opioid use, overdose history, past treatment and feelings about future treatment.
- 2) Education, Employment, Income and Housing: This assessment captures other demographic information related to subject's resources and social stability.
- 3) Overdose Risk Assessment: This assessment is used to determine the potential for future overdose based on prior overdose history, current drug use practices and social context for current drug use. This assessment is not standardized but is compiled from individual items of known risk factors for overdose.
- 4) World Health Organization Alcohol, Smoking and Substance Involvement Screening Test (WHO-ASSIST v.3). This is a multi-item tool to determine areas of substance use and misuse. This assessment battery screens for recent and lifetime use of a variety of substances, including illicit drugs, alcohol, pharmaceuticals and tobacco products.
- 5) EQ-5D-3L: This validated quality of life measure asks about problems in mobility, self-care, usual activities, pain and discomfort, anxiety and depression and overall health.

Locator information:

Subjects will be asked to provide a number of sources to ensure they can be contacted for follow-up visits. However, because we anticipate a number of subjects to have unstable housing, subjects may be enrolled if they provide at least one primary source of locator information.

Randomization

Subjects will be randomized to receive either standard of care or the study intervention. We will recruit equal numbers of subjects in the intervention and control arms of the study.

Follow-up Visits

Follow-up visits will occur at 1 and 6 months after enrollment. Interviews will be by phone or in-person. Assessments given at the baseline interview will be repeated at each follow-up point. In

addition to the assessments subjects will be asked questions in the intervention arm about how well the treatment navigation process is working.

Secondary Data Sources

Secondary data on health care and drug treatment utilization will be obtained from Washington State (separate IRB action pending) using the following sources:

- Division of Behavioral Health and Recovery (DBHR) data for drug treatment admissions data (formerly TARGET) and King County Behavioral Health and Recovery Division
- The Comprehensive Hospital Abstract Reporting System (CHARS) for hospital admissions
- Criminal History data extracted from Administrative Office of the Courts (AOC) and Department of Corrections (DOC) by the Washington Institute for Public Policy (WSIPP)
- Emergency Department Information Exchange data for emergency department visits administered by Collective Medical Technologies.

In the event of a subject death during the study we will request information on cause of death from the King County Medical Examiner's Office or Vital Records from Washington Department of Health. If we are unable to locate a subject during the course of the study or at final follow-up we will utilize the King County Jail Inmate Look-up Service. At no time will subjects be contacted or study procedures attempted while the subject is incarcerated.

Intervention Description

Subjects in the intervention arm will additionally begin a discussion with the interventionist about whether they are interested in treatment and medication choices for opioid use disorders. The interventionist, called a Treatment Navigator, will use a decision tool based on the SAMSHA guide to medication assisted treatment in order to help make an informed decision about treatment choices. A treatment decision may be made during the baseline visit or at some later visit. Once a decision is reached, the Treatment Navigator will meet with the subject periodically to assist with entering treatment and help with locating other social services as needed within the community. The meetings are neither structured nor scripted and the subjects will determine the agenda based on their areas of concern. The Treatment Navigator will, however, emphasize getting into treatment as quickly as possible once a decision is made. The Treatment Navigator and the subject will determine the schedule of meetings and will continue throughout the 6 month study period, with more visits anticipated at the start of participation, and fewer visits anticipated at the end. See Appendix A for the Treatment Decision Making Guide.

Study Medication

The medication, naloxone, is being used for an indicated condition, opioid overdose. The specific formulation of Naloxone we will use is Narcan® nasal spray, 4mg naloxone hydrochloride from ADAPT Pharma.

At usual doses, naloxone is relatively free of adverse effects. Because the duration of action of naloxone may be shorter than that of the narcotic being reversed, patients being treated for opioid intoxication with symptoms of respiratory depression should be closely monitored as additional doses of naloxone may be required.

Administration of naloxone to opioid-dependent patients may provoke an acute withdrawal syndrome (including body aches, diarrhea, tachycardia, fever, runny nose, sneezing, piloerection, sweating, yawning, nausea or vomiting, nervousness, restlessness or irritability, shivering or trembling, abdominal cramps, weakness, and increased blood pressure). Withdrawal reaction are not life threatening. Agitation and paresthesia have been infrequently reported with the postoperative use of naloxone hydrochloride injection.

Hypersensitivity reactions, such as allergic reactions, are theoretically possible, but have never been documented with naloxone. We will ask about allergic reactions to naloxone during the baseline interview and at each of the three follow up interviews. Any allergic reactions will be reported to the University of Washington's human subjects division.

Subjects will be educated about withdrawal reactions. The overdose intervention training and all education materials will clearly and strongly encourage calling 911 during any suspected overdoses. Emergency medical services are well equipped to handle any withdrawal reactions.

Regulatory Compliance and Safety

Regulatory binder

The regulatory files should contain all required documents, study-specific documents, and all important communications. Regulatory files will be checked for compliance prior to study initiation, throughout the study, as well as at study closure.

Study documentation includes all case report forms, data collection forms, workbooks, source documents, monitoring logs and appointment schedules, sponsor-investigator correspondence, and signed protocol and amendments, or Institutional Review Board correspondence and approved current and previous consent forms and signed participant consent forms.

Source documents include all reports and records necessary for the evaluation and reconstruction of the clinical research study. The original recording of an observation should be retained as the source document. Because direct data entry through the REDCap electronic data capture system will be employed relatively few source documents are anticipated for the collection of primary data.

Data Safety Monitoring Oversight Committee

The Data Safety Monitoring Oversight Committee will have 2-4 representatives who have clinical and research expertise relevant to the study. They are not directly involved in study procedures. They will meet during the period of study planning, one month and 4 months after the study is initiated. The committee will receive reports on the progress of the study prior to the meeting, including the number and characteristics of subjects and those who declined to participate. Any serious adverse events (SAE) will be discussed with the committee to determine if the risks of SAE could be modified by any changes in study procedures. Other reports will be provided as the committee requests. Committee membership will be determined prior to study initiation.

Drug accountability

Study medication will be ordered and prescribed by Kelly-Ross Pharmacy in Seattle. Upon receipt, the investigator is responsible for taking inventory of the investigational agent. A record of this inventory will be kept and usage will be documented. Any unused or expired investigational agent shall be accounted for.

Adverse event reporting

The risks expected from trials employing behavioral interventions are presumed minimal and the medication being prescribed for possible future use is designed to be used to prevent a fatal overdose with side effects being rare. However, given the nature of ongoing drug and/or medication use the population studied in this trial is possibly at risk for an overdose. Adverse events (AEs) will be categorized as serious or non-serious, as related or not related to the study, and as expected or unexpected. An AE is defined as any reaction, side effect, or untoward event that occurs during the course of the clinical trial. Stable chronic conditions, such as substance abuse, which are present prior to clinical trial entry and do not worsen, are not considered AEs. Common, minor ailments and complaints will be excluded from any type of documentation. These may include: colds, flu's, cuts, scrapes, coughs, headaches, stomach complaints, and general fatigue.

Serious adverse events (SAEs) are defined as any fatal event, any immediately life threatening event, any permanent or substantially disabling event, any event that requires or prolongs inpatient hospitalization, congenital anomaly or birth defect, or any event requiring intervention to prevent any of the previously listed serious events. Hospital visits that do not result in admittance are not considered SAE's (e.g. emergency room visit for a non- study-related injury that does not result in admittance). Normal childbirth and pre-planned elective procedures are not considered SAEs. AE/SAE's will be elicited by interventionists/research interviewers at each assessment visit by asking the participants if they have noticed any new problems or existing problems that have gotten worse (using the Adverse Events Worksheet).

Disclosure of an AE/SAE may also occur in an unsolicited manner to a research or clinical staff member. The interviewers should be focused on gathering data to aid in determining study relatedness. Study-relatedness will be determined by the interviewers in consultation with one of

the investigators. All AEs and SAEs will be recorded in the AE/SAE log and entered into the secured project database. AEs that are not study related do not require any further paperwork documentation besides the AE Log. In this study, potential AEs that may be related to the study would be an increase in emotional distress in relation to discussion of past or current drug use behaviors *or side effects of naloxone*.

University of Washington Adverse Events reporting requirements

The term adverse event is generally used to refer to any untoward or unfavorable medical occurrence in a human subject, including any abnormal sign (for example, abnormal physical exam or laboratory finding), symptom, or disease, temporally associated with the subject's participation in the research, whether or not considered related to the subject's participation in the research. Adverse events encompass both physical and psychological harms. They occur most commonly in the context of biomedical research although, on occasion, they can occur in the context of social and behavioral research.

Unanticipated problems, in general, include any incident, experience, or outcome that meets all of the following criteria:

1. unexpected (in terms of nature, severity, or frequency) given (a) the research procedures that are described in the protocol-related documents, such as the IRB-approved research protocol and informed consent document; and (b) the characteristics of the subject population being studied;
2. related or there is a reasonable possibility that the incident, experience, or outcome may have been caused by the procedures involved in the research; and
3. suggests that the research places subjects or others at a greater risk of harm (including physical, psychological, economic, or social harm) than was previously known or recognized.

The adverse event report form is to be used to report an adverse event where there is a reasonable probability that the event was attributable to a study procedure. The UW IRB defines reasonable probability as "more likely than not" - that is, there is a greater than 50% likelihood of the event having been caused or partially caused by the research or arising from the circumstances of the research.

Per HSD policy the form is required to be submitted as soon as possible but no later than 10 business days after becoming aware of the event.

Data security

Data will be uploaded to ADAI servers weekly. Only authorized individuals are permitted access to the project database. Data are backed up nightly so there is minimal risk of data loss. Any edits to previously saved data are fully tracked in an electronic audit table and include the date/time stamp

and user ID of the person making the edit. Ongoing data monitoring will be the responsibility of the research coordinator.

Confidentiality

We will obtain a federal Certificate of Confidentiality (CoC), protecting participants against disclosure of sensitive information (e.g., drug use). The Department of Health and Human Services (HHS) office that issues the CoC will be advised of any changes in the CoC application information.

Participant records will be kept confidential by the use of study codes for identifying participants on data collection forms, secure separate storage of any documents that have participant identifiers, and secure computing procedures for entering and transferring electronic data.

Study monitoring

The monitoring of study records will be conducted on a regular basis by the research coordinator. The purpose of these visits is to encourage and assess regulatory compliance and to document the integrity of the trial progress. Monitoring activity will assure that submitted data are accurate and in agreement with source documentation and will also review regulatory/essential documents such as correspondence with the IRB. Areas of particular concern will be participant informed consent, protocol adherence, safety monitoring, IRB reviews and approvals, regulatory documents, participant records, study drug accountability, and principal investigator supervision and involvement in the trial. The research coordinator will ensure that staff are trained and able to conduct the protocol appropriately and that study procedures are properly followed. If additional training of study personnel is needed, project staff will undertake or arrange for that training.

Data monitoring

Study data will be entered by interventionists directly into password protected, study specific laptop computers. Data will be captured using the REDCap electronic data capture system which uses a secure connection to local REDCap servers located at ITHS. Only authorized users will be allowed access to the data entry system and no identifiable data will be entered into REDCap. Research staff will use password protected UW works for data entry.

Data completion will be verified when study interviews are completed. Baseline data and study arm assignment will be captured by secure data servers at ITHS as data are collected in REDCap. Data will be managed by the principal investigator and research coordinator, who will access study data from desktop computers connected via local area network to computer servers that are in a locked room in a locked office suite at the Alcohol and Drug Abuse Institute (ADAI). Similarly, follow-up interview data will be entered directly into password protected, study specific laptop computers using REDCap, with data uploaded to servers at ADAI weekly.

Health services and cost data will be obtained, cleaned and made into analytic data sets by [name]. Data will be transferred securely and stored on ADAI servers which are backed up nightly. The research coordinator will be responsible for the integrity of all study data and will prepare

regular reports for the 3-person data and safety monitoring oversight committee which will review any adverse events as well as monitor study progress to ensure that study results are scientifically valid.

The research coordinator for the study will conduct software programming and data management activities. Data will be stored on computer servers at ADAI that are fully HIPAA-compliant in accordance with the University of Washington School of Medicine. The senior computer specialist at ADAI maintains nightly tape backups and active disaster recovery protection and procedures. The research coordinator will develop data collection forms used by research staff. These forms will also have a companion data dictionary which comprehensively defines each data element. The data dictionary specifies missing, illogical, out of range, and inconsistent value checks for each data element, in addition to logic checks and assists the project data analysis.

Intervention fidelity monitoring

The primary threat to the integrity of the intervention is that the intervention may not be delivered as intended. This potential problem is minimized because the intervention is highly structured and intervention fidelity will be regularly monitored by co-investigators who will monitor audio recordings of intervention sessions after the interventionist has initially been approved to conduct interventions without supervision.

Data Analysis Plan

Analyses will allow us to evaluate the aims of this study: 1) whether study procedures can be implemented with fidelity, 2) whether offenders can be enrolled and maintained in the study, 3) which medications/treatment options subjects select and their experiences and satisfaction with the interventions and 4) preliminary intervention effect size on outcomes of interest including recidivism, drug use, hospitalization, and treatment enrollment and retention. The number of subjects is not intended to be adequate to test the impact of the intervention, but rather to provide sufficient numbers of subjects to assess the feasibility of both research study procedures and intervention components.

The number and proportion of subjects retained at each step of the study will be documented and reported in a CONSRT diagram similar to the one in the Appendix for our current RCT. Baseline characteristics will be compared for each study arm to ensure randomization was properly implemented. Bi-variate test statistics of differences in outcomes of interest will be compared by study arm and reported for all outcomes. Study analyses will begin *prior* to study completion due to the fact that this is a pilot-feasibility trial and data will be used to determine if a full randomized trial is appropriate and what modifications to the study design are needed, this is different than procedures for a full RCT where analyses would await and complete, closed dataset. Data will be used to determine the possible treatment effect sizes which will allow sample size estimates to be calculated for a future full scale randomized controlled trial.

Equitable access to care and outcomes will be examined (Beletsky et al., 2015) by comparing the characteristics of the eligible pool of offenders with those screened, enrolled, and maintained throughout the study.

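### The death of a participant who is lost to follow-up can go unrecorded, because death records are requested only once a death is already known

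*Combined protocol and SAP*

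**What the plan says.** Secondary Data Sources has two adjacent provisions. The first concerns deaths: "In the event of a subject death during the study we will request information on cause of death", with the county medical examiner and state vital records as the sources. The second concerns participants who cannot be found, during the study or at its end: "at final follow-up we will utilize the King County Jail Inmate Look-up Service". No other step is named for a participant who cannot be found.

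Adverse event reporting makes a death a reportable event: "Serious adverse events (SAEs) are defined as any fatal event". It gives two ways of learning of such events. The active one is "AE/SAE's will be elicited by interventionists/research interviewers at each assessment visit by asking the participants". The passive one is "Disclosure of an AE/SAE may also occur in an unsolicited manner to a research or clinical staff member".

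The Data Safety Monitoring Oversight Committee section says "Any serious adverse events (SAE) will be discussed with the committee", and sets meetings during planning and at one month and 4 months after the study starts. Data monitoring adds regular reports to the committee from the research coordinator.

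On contact, Follow-up Visits says "Follow-up visits will occur at 1 and 6 months after enrollment" for both arms. Intervention Description adds, for the intervention arm only, "The Treatment Navigator and the subject will determine the schedule of meetings and will continue throughout the 6 month study period".

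The Data Analysis Plan reports retention at each step in a flow diagram and compares outcomes by arm with bivariate tests. It gives no rule for deaths.

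**The concern.** The plan says what to do after a death is known, but not how a death becomes known. The people most likely to be lost are those whose deaths the active route cannot find, because a participant who has died cannot be asked about adverse events. Loss is foreseeable: the Locator information section expects unstable housing and allows enrolment with a single contact source.

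Three things are at stake.

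- **Safety.** The Introduction cites the raised risk of fatal overdose after release as part of the reason for the study. The oversight committee can discuss only the deaths it hears about.
- **Retention.** Whether participants can be kept in the study is a stated aim. A death filed as dropout misstates the answer.
- **Linked outcomes.** A participant who died unnoticed has no later arrests or admissions, so could be read as free of recidivism or hospitalisation.

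**Working it through.** **Step 1: the routes by which a death could be recorded.**

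| Route in the plan | Would it find the death of a lost participant? |
|---|---|
| Medical examiner or vital records | Only if the death is already known |
| Jail look-up when someone cannot be located | No; it shows custody |
| Asking the participant at a visit | No |
| Unsolicited disclosure to staff | Possibly, by chance |
| Linked treatment, hospital, criminal history and emergency data | Possibly, but not described as a source of deaths; IRB action on this linkage is pending |
| Locator contacts, community corrections | Possibly, but not assigned this task |

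No planned step reliably closes the gap.

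**Step 2: how often at least one death would be missed.** The plan gives n = 100 in two equal arms, so 50 per arm. It gives no mortality or detection rate, so there is no figure to reproduce. The following are assumptions: six-month mortality q of 0.5%, 1% or 2%, and a share u of deaths unnoticed of 25% or 50%.

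- P(at least one death) = 1 − (1 − q)^100
- P(at least one missed death) = 1 − (1 − q·u)^100

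| q | At least one death | At least one missed, u = 25% | At least one missed, u = 50% |
|---|---|---|---|
| 0.5% | 39% | 12% | 22% |
| 1% | 63% | 22% | 39% |
| 2% | 87% | 39% | 63% |

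For example, with q = 2% and u = 50%: 1 − 0.99^100 = 0.634.

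A second model gives similar values. If 20 of 100 participants are lost and carry the same risk as the rest, the chance of at least one death among them is 1 − (1 − q)^20. That is 18%, 33% or 56% at assumed mortality of 1%, 2% or 4%.

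**Step 3: effect on another outcome.** Take an arm of 50 with one unnoticed death and 15 events among the 49 living. Leaving the death in as event-free changes 15/49 = 30.6% to 15/50 = 30.0%, a shift of 0.6 points.

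**Step 4: could detection differ by arm?** Assume equal true mortality, with 90% of deaths noticed in the intervention arm and 60% in control. Recorded deaths are then binomial(50, 0.9q) and binomial(50, 0.6q).

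| q | More recorded in intervention | More recorded in control | Tied |
|---|---|---|---|
| 0.5% | 18% | 11% | 71% |
| 1% | 29% | 18% | 54% |
| 2% | 41% | 23% | 36% |

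The detection rates have no basis in the documents, and exchanging them between arms exchanges the second and third columns. The table shows that a difference is possible, not that one is expected.

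**Step 5: timing.** The last scheduled committee meeting is 4 months after the study starts. If the study starts with the first enrolment, no participant completes 6 months before that meeting. A search made only at the end of follow-up would therefore come after every scheduled meeting.

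**The case against.** The strongest reply is that deaths have other ways of surfacing. Every participant is released to community corrections supervision, and people not planning to be in King County or to report to corrections there for 6 months are excluded. Recruitment and some interviews take place in corrections offices. Supervision covers both arms, so controls are not out of sight between months 1 and 6. Locator contacts and linked records may reveal further deaths. This stands as a reason not to say that deaths will be missed. It does not close the gap, because nothing in the plan asks these sources about vital status or says they will report a death.

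A reader might infer that the intervention arm will look less safe because its navigator notices more deaths. The documents do not support that. Meetings follow a mutually agreed schedule with fewer expected late on, the detection rates are unknown, death is not a listed outcome, and no between-arm mortality test is planned.

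A reader might also infer that interviews falling due in custody materially bias the drug-use comparison, since contact is barred then and no visit window is stated. Assume true use of 60% in control and 45% in intervention, with 5% of non-users in custody and 20% (control) against 10% (intervention) of users. Observed use is 0.48/(0.48 + 0.38) = 55.8% against 0.405/(0.405 + 0.5225) = 43.7%. The difference is 12.1 points instead of 15, a shift of 2.9. The 95% half-width at 50 per arm is 1.96 × √(0.24/50 + 0.2475/50) = 19.4 points. For a pilot not sized to test impact, a visit window or a bounds analysis is mainly a matter of detail or preference.

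Finally, the flow diagram is to follow one from another trial that is not shown here, so it may already separate deaths from other loss. That would help with reporting known deaths but not with finding unknown ones.

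**Conclusion.** The gap is real and should be fixed. As written, death records are consulted only after a death is known, and the search for a missing participant does not look for death. A lost participant's death can therefore go unrecorded. Under assumed mortality of 0.5% to 2%, with a quarter to a half of deaths unnoticed, the chance of missing at least one among 100 is about 12% to 63%. All these rates are assumptions.

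The loss is mainly of safety and retention information. Other outcomes barely move, so a reader should not conclude that the pilot's effect estimates are seriously distorted. Detection could differ by arm, but the size and direction are unknown. The text check is firm; the magnitude is only indicative.

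**What to change.** 1. Whenever a participant cannot be located, check the medical examiner and vital records as well as the jail look-up. Report any death found to the oversight committee when it is found, not only at a scheduled meeting.
2. After the last 6-month window, once records for it are available, search the same two sources for all 100 participants in both arms, whether or not a death is suspected.
3. Report deaths by arm as their own category, separate from dropout. Do not count them as event-free or as non-users, and leave them out of the denominator of any drug-use percentage among the living.

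Reporting custody separately from other loss would be a useful but optional addition.

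The cost is one batch request, single look-ups for people not located, and wording for the IRB and the participants' authorisation. Two limits remain: record lag may delay the early look-ups, and deaths outside Washington can still be missed.
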